c. Describe how data and specimens will be handled:	□ N/A	
i. What information will be included in that data or associated with the spe	cimens?	
All specimens will be collected with deidentified information. Specifically, the ID, date, specimen type (i.e. serum or plasma), and analyte to be measured will be included on the tube label.		
ii. Where and how data and/or specimens will be stored?		
Data are stored in subject folders, specimens are stored de-identified in -80 freezers		
iii. How long will the data and/or specimens be stored?		
Until analyzed		

iv.	Who will have access to the data or specimens?
	All investigators who are on the protocol
v .	Who is responsible for receipt or transmission of the data and/or specimens?
	[name]
vi.	How will data and/or specimens be transported?
	According to biosafety procedures

8. Provisions to Monitor the Data to Ensure the Safety of Subjects

This study involves no more than minimal risk study and this section is not required. \Box N/A

The plan might include establishing a data monitoring committee and a plan for reporting data monitoring committee findings to the IRB and the sponsor.

a. Describe the plan to periodically evaluate the data collected regarding both harms and benefits to determine whether subjects remain safe.

Subjects will be monitored the entire time they are in the LIVEP lab. The PI and study team will evaluate the safety for each participant by changes in BP and HR before, during and after treatment.

b. Describe what data are reviewed, including safety data, untoward events, and efficacy data.

During consenting we ask what drugs they are currently taking and we also ask on every visit if there have been any changes to the drugs. We will frequently monitor BP, and HR to determine how the treatment is affecting them.

c. Describe how the safety information will be collected (e.g., with case report forms, at study visits, by telephone calls with participants).

Data is consistently collected during their visits which will monitor how their body is reacting to the drug or cocktail treatment.

d. Describe the frequency of data collection, including when safety data collection starts.

This done with every visit, subjects BP, and HR are consistently monitored during the duration of their visit

e. Describe who will review the data.

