The PI will review the data on a daily basis. Because Biomarin is the manufacture of Kuvan and is providing the drug for this study, the researchers may also disclose information to BioMarin Pharmaceutical Inc.

f. Describe the frequency or periodicity of review of cumulative data.

This will be evaluated during each visit.

g. Describe any conditions that trigger an immediate suspension of the research.

If the PI thinks that the study is causing harm to the participant they will withdraw that subject from the study.

Withdrowal of Subjects

. withdrawar of Subjects	
In the event that participating in the study might be harmful to the subject's health and well-being, we will end their study participation. In addition, if we feel that the participants are not adhering to the treatment we have the right to end their study participation. At any time, the subjects also have the right to stop participating in the study.	I □ N/A
For any reason the subjects ask to withdraw from the study they will be paid an hourly rate of \$10.00 an hour.	□ N/A
	□ N/A

10. Risks to Subjects

All procedures in this study have been routinely performed in research studies in the past and are of low risk to participants.

Venous Blood Draw. Potential risks related with taking a blood sample are few but include slight bruising, pain, a temporary feeling of faintness, and phlebitis. Rarely, there may be a small blood clot or infection at the site of the needle puncture. All blood draws will be performed by a research team member or a nurse who is certified in drawing blood; in either case sterile techniques will be used.

Pulmonary Function Test. There are no known risks associated with this test.

Muscle Function Test. Electrical stimulation of the muscles may be uncomfortable and could be painful. If the muscle stimulation is too painful, we will adjust the stimulation to a level that the subject can tolerate. The study does not require the stimulation to be painful for the study to be successful. Because the stimulator "exercises" the muscle, the muscle may be sore for a few days following the protocol.

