Adverse event information will be collected in an ongoing fashion through patient reporting AEs to their physician or health care provider. Seriousness and relatedness will be assessed by the treating physician, with appropriate reporting.

A designated primary contact person based at the treatment center will be responsible for the collection and reporting of AEs for patients participating in the program.

Serious Adverse Events

A serious adverse event (SAE) is defined as any AE that:

- Results in death
- Is life threatening, that is, places the subject at immediate risk of death from the event as it occurred. This definition does not include a reaction that, had it occurred in a more severe form, might have caused death
- Requires in-patient hospitalization or prolongation of an existing in-patient hospitalization. Admission of a subject to the hospital as an in-patient as a result of an AE, even if the subject is released on the same day, qualifies as hospitalization
- Results in persistent or significant disability or incapacity. An event qualifies as resulting in a persistent or significant disability or incapacity if it involves a substantial disruption of the subject's ability to carry out usual life functions. This definition is not intended to include experiences of relatively minor or temporary medical significance.
- Is a congenital anomaly or birth defect, an AE that occurs in the child or fetus of a subject exposed to the product prior to conception or during pregnancy
- Important medical event that does not meet any of the above criteria, but may jeopardize the subject or require medical or surgical intervention to prevent one of the outcomes listed above.

More than one of the above criteria may apply to any specific event.

Pregnancy

Pregnancy in a subject being treated with the product should be reported immediately (within 24 hours of becoming aware of the pregnancy) to BioMarin Pharmacovigilance by using the FDA 3500A (MedWatch Form). Every effort should be made to follow the patient through resolution of the pregnancy (termination or delivery) and report the resolution of the FDA 3500A (MedWatch Form) to BioMarin Pharmacovigilance.

SAE and Pregnancy Reporting

In Investigator IND studies,

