KUVAN[™] serious, related, unlabelled, (unexpected) adverse events will be reported to the FDA as required by 21 CFR 312.32 by the Investigator/Sponsor. These reports may be filed utilizing the Form FDA 3500A (MedWatch form). The Investigator/Sponsor will provide BioMarin Pharmacovigilance, with a copy of this report.

All serious adverse events (SAEs) and pregnancy reports whether or not considered drug-related should be reported to BioMarin Pharmacovigilance (contact information below) within 24 hours of receipt by the investigator/sponsor by using the FDA 3500A (MedWatch Form).

For Comparator Drugs / Secondary Suspects (Concomitant Medications), all serious adverse experiences will be forwarded to the product manufacturer.

For Comparator Drugs / Secondary Suspects (Concomitant Medications), all serious adverse experiences will be forwarded to the product manufacturer.

Clinicians should not wait to collect additional information that fully documents the event before notifying BioMarin's Pharmacovigilance Department of an SAE or pregnancy. BioMarin may be required to report certain SAEs to regulatory authorities within 7 calendar days of being notified about the event; therefore it is important that clinicians submit additional information requested by BioMarin Pharmacovigilance as soon as it becomes available.

Reporting of SAEs to the IRB will be done in compliance with the standard operating procedures and policies of the IRB and with applicable regulatory requirements.

Contact information for BioMarin's Pharmacovigilance Department is as follows:

BioMarin Pharmaceutical Inc. [name] [contact] [contact] Email: [contact]

Product Complaints Reporting

A product complaint ("Complaint") is any direct, written, electronic, or oral communication of dissatisfaction that alleges deficiencies related to the identity, quality, durability, labeling, purity, stability, appearance, effectiveness, safety, and/or design of a drug product after it is released for distribution.

Complaints that simultaneously fall under Adverse Event definitions under this Protocol need only be reported via the Adverse Event reporting procedure set forth in this Protocol.

Investigator or designee (Reporter) shall capture the following Complaint information as relates to Kuvan used under this Protocol:

- Date complaint received
- Product Name and Lot Number
- Indicate if the product is available for return to BioMarin for investigation

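### Adverse event (AE) collection relies on patients volunteering symptoms: no visit has a stated AE question, and the handover from physician to the named contact person is not described

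*Combined protocol and SAP*

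**What the plan says.** Section 10, Adverse Events, gives the collection method: "Adverse event information will be collected in an ongoing fashion through patient reporting AEs to their physician or health care provider". The treating physician then assesses seriousness and relatedness. The next paragraph names an owner: "A designated primary contact person based at the treatment center will be responsible for the collection and reporting of AEs". The same section defines an AE broadly; any unfavorable symptom counts, whether or not it is thought related to treatment.

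Section 8 covers safety monitoring at visits. Item 8a: "The PI and study team will evaluate the safety for each participant by changes in BP and HR before, during and after treatment". Item 8b adds that current drugs are asked about at consent and that "we also ask on every visit if there have been any changes to the drugs". Item 8c, which asks how safety information is collected, is answered in general terms: "Data is consistently collected during their visits which will monitor how their body is reacting to the drug or cocktail treatment". Items 8d and 8f place this at every visit, and 8e says "The PI will review the data on a daily basis". The action on harm is in 8g: "If the PI thinks that the study is causing harm to the participant they will withdraw that subject from the study".

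The Kuvan paragraphs in Section 6 (Risk Assessment) and Section 10 list the same six risks: headache, nausea, vomiting, diarrhea, abdominal pain and upper respiratory tract infection. Section 14 says subjects with questions or concerns must contact the team at once. For serious events, the report to the manufacturer is due "within 24 hours of receipt by the investigator/sponsor by using the FDA 3500A (MedWatch Form").

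**The concern.** Five of the six listed Kuvan risks are symptoms that a patient feels and must mention, and the sixth is a common infection that is usually noticed the same way. Blood pressure and heart rate do not record any of them. A question about drug changes finds them only if the patient took something for the complaint. Without a scheduled question, a symptom enters the record only if the patient raises it with a physician or with the team. If it goes to a physician, it must also be passed on.

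The harm review in item 8g can use only what reaches the principal investigator. The study is open-label and tests several doses of a drug that Section 10 says is not approved for COPD, so an incomplete symptom record is a real loss even in a pilot. The gap mainly concerns non-serious events. Serious events have detailed reporting rules once the team knows of them.

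**Working it through.** The plan gives no figure to reproduce here, so the main check sets the text side by side.

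**1. Do the named visit items measure the listed risks?** Named in Section 8: blood pressure, heart rate, current drugs and drug changes. Listed risks: six. Risks directly measured by a named item: 0 of 6. The drug question can pick up some of them indirectly.

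**2. Is an AE question scheduled?** The testing-day list in Section 6 has consent, pulse wave velocity, flow-mediated dilation, skin blood flow with local heating, blood draw and pulmonary function. It has no AE item. Section 8c offers case report forms, visits and telephone calls as examples; the answer refers to visits but names no form and no question. Stated AE questions: 0.

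**3. Which routes exist, and who starts them?**
- Patient to physician or provider (Section 10): started by the patient.
- Physician to contact person (Section 10): an owner is named; no mechanism or timing is stated.
- Patient to study team (Section 14): started by the patient.
- Visit review (8a to 8f): started by the team, but the only named content is that in step 1.

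The only route started by the team has no stated symptom content. That sits poorly with an AE definition that includes any unfavorable symptom.

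**4. How much would a visit question add?** Inputs: 12 Kuvan and 12 antioxidant patients (Section 4), and five experimental visits at baseline and weeks 4, 8, 12 and 16 (Section 6, Visits Required). A subject may take part in both protocols, so 24 counts patient courses.
- Baseline enquiries: 24 x 1 = 24.
- Later enquiries: 24 x 4 = 96, of which 12 x 4 = 48 are in the Kuvan protocol.
- Total: 24 + 96 = 120 if every visit is attended.
- Longest wait from onset to the next question: 4 x 7 = 28 days. If onset is uniform between visits (an assumption), the mean wait is 28 / 2 = 14 days.

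**5. What would it not deliver?** Assume the 12 Kuvan patients split equally over three doses: 12 / 3 = 4 per dose. If none of 4 reports an event, the one-sided 95% upper limit solves (1 - p)^4 = 0.05, so p = 1 - 0.05^(1/4) = 1 - 0.473 = 0.527. Even with complete capture, 0 of 4 is compatible with a rate up to about 53%.

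**6. What was left uncomputed.** The number of events missed under the present method needs a capture share, and the documents give none. The one frequency they give is about 4% in Section 6 and 4% or more in Section 10, from patients treated for another disease. It can be read per symptom or for the six together. An expected shortfall built on it would be invented.

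**The case against.** The strongest reply is that the protocol does more than the passive sentence suggests. It names a person responsible for collecting and reporting AEs, tells subjects to contact the team directly, and states that safety data are collected and reviewed at every visit, with daily review by the principal investigator. Section 15 has a study doctor on hand. All of this stands, and it rules out some stronger readings.

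- A reader might infer that there is no path from patient to study team. The documents do not support that: Sections 10 and 14 give one. What is missing is how and when a physician's information reaches the contact person.
- A reader might infer that AEs go only to an outside family physician. The text refers to the patient's physician or provider and to the treating physician. Patients are recruited from university-associated clinics, so these could be clinicians close to the study. The wording is ambiguous.
- A reader might infer that visits collect nothing beyond blood pressure, heart rate and drug changes. Items 8c to 8f are broader than that; they simply name nothing else. The consent pages are not in the file, so instructions given there cannot be counted as absent.
- A reader might infer that the 24-hour rule for serious events is defective. A reporting duty can begin only when the reporter knows, and Section 10 tells clinicians not to wait before notifying the manufacturer. It remains true that any delay before receipt falls outside the 24 hours.

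The objection does not supply a scheduled symptom enquiry. A named owner and a daily review work only on reports that arrive.

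**Conclusion.** The concern holds in a limited form and counts as a cheap improvement. As written, no AE question is stated for any visit, the named visit items directly measure none of the six listed Kuvan risks, both patient routes depend on the patient starting them, and the handover to the contact person is undescribed. Non-serious symptoms may therefore escape the harm review.

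The documents do not show that events will be lost in any particular number, or that serious events go unreported. The conclusion rests on reading Section 8 as naming all its visit safety items. If staff already ask about symptoms under the general wording of 8c, the remedy is only to write that down. The enquiry count assumes full attendance, and the 53% limit assumes equal allocation to the three doses.

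**What to change.** At every experimental visit (baseline and weeks 4, 8, 12 and 16), have existing staff ask one open, non-leading AE question, worded identically in both protocols, next to the drug-change question. The baseline answer records symptoms already present. Record onset and seriousness, pass the record to the contact person and the principal investigator, and list events descriptively by protocol and dose. Because Section 6 lets procedures be omitted on a testing day for time, state that this question is always asked.

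If a symptom checklist is added, use the same one in both protocols. Prompting Kuvan patients alone would make ascertainment unequal and the listing by protocol hard to interpret.

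Keep the ongoing patient and physician reporting and the Section 14 instruction, and state how and when a physician's report reaches the contact person. A four-weekly question does not replace prompt reporting of serious events.

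The cost is a few minutes per visit and one line on a form, with no extra staff. The question relies on four-week recall, so short-lived symptoms may still be missed, and event rates by dose remain inestimable.
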